##### 14.3.2.2 Fungal infections

Fungal infections will be summarized separately based on all TEAEs coding to the high level group term (HLGT) = 'Fungal infectious disorders'.

##### 14.3.2.3 Opportunistic infections

Opportunistic infections (including tuberculosis) will be summarized in a stand-alone table. The table will include all TEAEs identified using UCB-defined search criteria (refer to Excel spreadsheet on "OI - MedDRA v19.0.xlsx" in "Bimekizumab-Safety-Topics-of-Interest.docx").

The following steps are followed for identifying opportunistic infections:

**Step 1:** Refer to column B of the spreadsheet which identifies the Preferred Terms (PTs) to be classified as opportunistic infections using either a single 'x' or a double 'xx'.

- TEAEs which code to a PT flagged with a single 'x' need to also be serious to be considered an opportunistic infection.

- All TEAEs which code to a PT flagged with a double ‘xx’ are considered to be an opportunistic infection, regardless of seriousness.

All serious TEAEs in the study database which code to a PT flagged with a single ‘x’ and all TEAEs in the study database which code to a PT flagged with a double ‘xx’ will be summarized as an opportunistic infection in the stand-alone table.

Step 2: Refer to column C of the spreadsheet which identifies the PTs that need to be evaluated on a case-by-case basis by the study physician to determine whether it is a true opportunistic infection or not. The process for physician review is as follows:

1. Study programming team creates a spreadsheet which lists all of the subjects with a TEAE present in the database which codes to a PT identified as case-by-case. Information from the AE dataset to be included in the spreadsheet: Subject ID, AE verbatim term, SOC, High Level Term (HLT), Lower Level Term (LLT), PT, AE start date, AE end date, seriousness, severity, relationship to study medication, action taken. Additionally, a column will be included where the study physician can document their decision on the case.
2. Study physician reviews the cases in the spreadsheet and indicates in the additional column which AEs are confirmed to be opportunistic infections via a single ‘x’.
3. At quarterly Infectious Disease Committee (IDC) Meetings, outputs will be produced and reviewed by the study physician ahead of the IDC Meeting. The IDC will then agree on the final adjudication for each potential opportunistic infection. A final output for opportunistic infections will be produced and agreed upon between the study physician and the IDC prior to finalizing the database.
4. Study programming team incorporates these decisions into the AE dataset by merging the final decisions for individual subjects / PTs and flagging the confirmed opportunistic infections as such in the dataset.

All subjects with a case-by-case PT reported that has been confirmed by the study physician to be an opportunistic infection in Step 2 will be summarized as such in the stand-alone table, along with all events identified in Step 1 of this process.

The timing and frequency of Step 2 will be outlined and agreed to by the study team at the beginning of the study. It is suggested that this process be executed multiple times throughout the course of the study, more frequently in the weeks prior to the DMC meeting.

Following the initial physician review of case-by-case events, subsequent reviews will be based on the cumulative set of case-by-case events present in the database at each time point of spreadsheet creation. Physician decisions from previous runs should be retained in each subsequent run. The final run of the spreadsheet, with all final study physician decisions (with IDC agreement) on the full set of case-by-case events, will be archived at the conclusion of the study.

### **14.3.3 Malignancies including lymphoma**

Malignancies will be presented in 2 separate tables based on the following SMQs:

- Malignant or unspecified tumours
- Malignant tumours

Events included in the ‘Malignant tumours’ tabulation will be a subset of the events in the ‘Malignant or unspecified tumours’ tabulation. The SMQ search should include all TEAEs which code to a PT included in the Scope=Narrow group within each SMQ.

The output tables will include 2 different overall incidence rows:

- The first overall incidence row will summarize ‘Any malignancies (including unspecified)’ or ‘Any malignancies’ (depending on the table) and this row will summarize the incidence of all AEs flagged for inclusion in the table, regardless of the HLT it codes to.
- The second overall incidence row will summarize ‘Any malignancy (including unspecified, excluding non-melanomic skin cancers)’ or ‘Any malignancy (excluding non-melanomic skin cancers)’ (depending on the table) and this row will summarize the incidence of AEs flagged for inclusion in the table, excluding those which code to an HLT of ‘skin neoplasms malignant and unspecified (excl melanoma)’.

#### **14.3.4 Cytopenias**

Cytopenias will be tabulated separately based on the SMQ = ‘Haematopoietic cytopenias’. Serious and non-serious TEAEs will be included in the tabulation. The SMQ search should include all serious TEAEs which code to a PT included in the Scope=Broad and/or Scope=Narrow groups within the SMQ.

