### 9.6 Adverse events for special monitoring

UCB has identified AEs for special monitoring (AESM). An AESM is an AE or safety topic for which special monitoring, additional data collection activities, and/or enhanced signal detection activities (within UCB), are considered appropriate. Identified AESM can be of particular interest based on findings from the IMP clinical program to date, potential risks generally associated with biologic immunomodulators, or comorbidities and risk factors prevalent in the study population.

Adverse events for special monitoring for this study include: serious infections (including opportunistic infections and TB; see [Section 9.8.1](#)), cytopenias, hypersensitivities, suicide ideation or behavior (assessed using the C-SSRS; see [Section 9.8.6](#)), depression and anxiety (assessed using the HADS; see [Section 12.4](#)), major cardiovascular events, and liver function test changes/enzyme elevations (ALT, AST, bilirubin; see [Section 9.7.1](#)), malignancies, and inflammatory bowel diseases.

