### 11.2.3 Presentation of adverse events

An overview of the number and percentage of subjects who experience TEAEs will be presented based on the SS. This tabulation will include the number and percentage of subjects with any TEAEs, serious TEAEs, related TEAEs, discontinuation due to TEAEs, severe TEAEs, AEs leading to death and TEAEs leading to death; event counts will also be included.

- The tabulation will be presented by PS0018 dose at onset.
- This tabulation will be repeated by Dose adjustment and PS0016 randomized treatment group.

In addition, the following summaries will be presented by PS0018 dose at onset, SOC, high level term (HLT) and PT, based on the SS:

- Incidence of TEAEs by PS0018 dose at onset, including the EAIR and EAER calculated as described in [Section 11.2.2](#) for the 'Any TEAE' category only
- Incidence of TEAEs by PS0018 dose at onset, including the EAIR and EAER calculated as described in [Section 11.2.2](#) for the 'Any TEAE' category only by overall ADA status (positive/negative)
- Incidence of TEAEs by Dose adjustment and PS0016 randomized treatment group
- Incidence of serious TEAEs by PS0018 dose at onset and Dose adjustment
- Incidence of TEAEs by relationship and PS0018 dose at onset
- Incidence of TEAEs by maximum relationship and PS0018 dose at onset
- Incidence of TEAEs by maximum intensity and PS0018 dose at onset
- Incidence of fatal TEAEs by relationship and PS0018 dose at onset

- Incidence of serious TEAEs by relationship and PS0018 dose at onset
- Incidence of non-serious TEAEs above threshold of 5% of subjects by PS0018 dose at onset
- Incidence of non-serious TEAEs above threshold of 5% of subjects by relationship and PS0018 dose at onset
- Incidence of ongoing AEs from PS0016
- Incidence of ongoing AEs from PS0016 which do not worsen in severity, or AEs started prior to PS0018 dose, by PS0016 randomized treatment group

In addition, separate AE summaries by PS0018 dose at onset, SOC, HLT and PT will be included for the following AEs of special monitoring (AESM) further defined in [Section 14.3](#).

- Major cardiovascular events
- Serious infections, including opportunistic infections and tuberculosis (TB)
- Malignancies including lymphoma
- Cytopenias
- Neuropsychiatric events (in particular, depression and suicide)
- Inflammatory bowel disease
- Anaphylactic reaction (hypersensitivity and anaphylactic reactions)
- Hepatic events and drug-induced liver injury

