All summary tables (including those for AESM) will contain the number and percentage of subjects and the number of events where applicable. A subject who has multiple events in the same SOC, HLT and PT will be counted only once in the subject counts but all events will be included. In addition, for all tabulations of AESM, the EAER and EAIR will be reported only for the categories 'Any TEAE'.

The criteria for identifying AESM and additional criteria for reporting AESM are provided in [Section 14.3](#).

Adverse event summaries will be ordered by alphabetical SOC, alphabetical HLT within SOC and decreasing frequency of PT in the 'BKZ 320mg' column for the PS0016 randomized treatment group. In the PS0018 dose at onset tables, the summaries will be presented in a similar manner in decreasing frequency of PT in the 'All BKZ' column.

For tables including only number and percentage of subjects, summaries will be ordered by alphabetical SOC, alphabetical HLT within SOC and decreasing incidence of PT within HLT and SOC in the 'All BKZ' column.

Any adverse events considered ongoing from PS0016 which do not worsen in severity during PS0018 dosing, or starting prior to first PS0018 dose will not be considered treatment emergent in PS0018 and will be tabulated separately.

The AEs will be listed by PS0016 randomized treatment group and include all subjects screened in the ES. The listing will include the onset date/time and outcome date/time of the event (including relative days), the AE duration (derived), dose at onset, days since first dose of study

medication, days since most recent dose of study medication, pattern of event, intensity, relationship, action taken and outcome. In addition the listing will flag AEs that led to discontinuation, TEAEs, AESM, AEs of special interest (as reported on the eCRF) and SAEs.

A glossary of all TEAE terms will be provided including the SOC, HLT, PT and reported term.

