### 14.3 Adverse events of special monitoring

The following AESM are defined for bimekizumab and will be summarized separately as described in [Section 11.2.3](#):

- Major cardiovascular events
- Serious infections, including opportunistic infections and tuberculosis (TB)
- Malignancies including lymphoma
- Cytopenias
- Neuropsychiatric events (in particular, depression and suicide)
- Inflammatory bowel disease
- Anaphylactic reaction (hypersensitivity and anaphylactic reactions)
- Hepatic events and drug-induced liver injury

All AESM tabulations will be presented by Treatment at onset, SOC, HLT and PT, based on the SS, and will include the EAIR and EAER in the 'Any TEAE' categories only.

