#### **14.3.5 Neuropsychiatric events**

This table is based on the SMQ of “Depression and suicide/self-injury” (all TEAEs that code to a PT included in the Scope=Broad and/or Scope=Narrow).

An external neuropsychiatric adjudication committee will evaluate potential neuropsychiatric events and determine whether any of those events were associated with suicidal ideation and behavior (SIB). If an event is adjudicated as SIB, further information will be provided. A separate listing for SIB events as determined by the adjudication committee will be included.

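### SAP 14.3.4 contradicts itself: the cytopenia table is meant to hold serious and non-serious TEAEs, but the search that fills it selects serious ones only

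*SAP*

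**What the plan says.** SAP 14.3.4 builds the cytopenia table from a single source, the MedDRA query for haematopoietic cytopenias. On content it says: "Serious and non-serious TEAEs will be included in the tabulation". On selection it says: "The SMQ search should include all serious TEAEs which code to a PT included in the Scope=Broad and/or Scope=Narrow groups within the SMQ".

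Two neighbouring special-monitoring sections also use MedDRA query searches. For malignancies (SAP 14.3.3): "The SMQ search should include all TEAEs which code to a PT included in the Scope=Narrow group within each SMQ". For neuropsychiatric events (SAP 14.3.5): "all TEAEs that code to a PT included in the Scope=Broad and/or Scope=Narrow". Neither has a seriousness filter.

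Protocol 9.6 names the topics for special monitoring. The list includes "cytopenias, hypersensitivities, suicide ideation or behavior" with no seriousness limit on cytopenias, although infections in the same list are limited to serious ones.

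On rates, SAP 14.3 presents the special-monitoring tables "by Treatment at onset, SOC, HLT and PT, based on the SS, and will include the EAIR and EAER" for the any-TEAE categories. SAP 11.2.3 likewise says that "for all tabulations of AESM, the EAER and EAIR will be reported only for the categories" of any TEAE. The general TEAE table in 11.2.3 gives exposure-adjusted rates "for the 'Any TEAE' category only".

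**The concern.** The content sentence and the search sentence cannot both be followed literally. The search is the only stated source of events for the table. Run as written, it does not return the non-serious events that the table is required to contain.

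This table carries the SAP's only exposure-adjusted incidence rate (EAIR) and event rate (EAER) specific to cytopenias, shown by PS0018 dose at onset. The general TEAE table gives these rates only for any TEAE overall. In the general tables, individual cytopenia preferred terms appear as counts, without rates and not grouped by the MedDRA query. Laboratory output is no substitute: SAP 11.3 presents the by-visit hematology summaries and the Grade 3-and-above table by PS0016 randomized group, not by PS0018 dose.

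The topic is relevant to this drug. Protocol 2.2.1 reports a fall in mean neutrophil count on active treatment in the psoriatic arthritis study, described there as not clinically relevant. A mild effect of that kind could appear mainly as non-serious events.

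**Working it through.** **Comparison of the texts**

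| Place | Which events |
|---|---|
| SAP 14.3.4, content sentence | serious and non-serious |
| SAP 14.3.4, search sentence | serious; broad and/or narrow scope |
| SAP 14.3.3, malignancy search | all TEAEs; narrow scope |
| SAP 14.3.5, neuropsychiatric search | all TEAEs; broad and/or narrow scope |
| Protocol 9.6 | cytopenias, no seriousness limit |

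The search sentence is the only entry that limits cytopenias to serious events. The SAP's amendment log supports the same reading of intent. Change #8 altered the content sentence from serious only to serious and non-serious, and no change to the search sentence is logged. The log is used here only as evidence of intent; the conflict lies between two sentences of the current text.

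**Direction of the effect.** With the serious-only search, the numerators of the subject count, EAIR and EAER are equal to or lower than those for all cytopenias. The EAIR denominator is equal or higher, because time at risk runs on past a non-serious event. The EAER denominator does not change.

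**Size per omitted subject.** The plan gives no cytopenia figure to reproduce. The inputs from the documents are:

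- up to 45 subjects (Protocol 14.7);
- last scheduled dose at Week 44 (SAP 3.2.1.2);
- time at risk = last dose date − first dose date + 140 days (SAP 11.1.2);
- 365.25 days per year (SAP 11.1.2);
- EAIR = 100 × n / total subject-years, with exact limits χ²(2n, 0.025)/2 and χ²(2(n+1), 0.975)/2, each divided by subject-years (SAP 11.2.2), then × 100.

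*No dropout (upper bound on exposure):*
- Days per completer: 44 × 7 + 140 = 448.
- Total: 45 × 448 / 365.25 = 55.2 subject-years.
- One affected subject, with onset assumed at 10% to 90% of follow-up: EAIR 1.85 to 1.82 per 100 subject-years.
- No events: 0, with upper limit 100 × 3.689 / 55.2 = 6.68.

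*Assumed 20% leaving at Week 12 with last dose at Week 8 (9 of 45):*
- Days per leaver: 8 × 7 + 140 = 196.
- Total: (36 × 448 + 9 × 196) / 365.25 = 49.0 subject-years.
- One affected subject, same onset range: EAIR 2.09 to 2.05.
- No events: 0, with upper limit 100 × 3.689 / 49.0 = 7.53.

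Here 3.689 is χ²(2, 0.975)/2. These figures are for the all-bimekizumab column. The dropout share and onset times are assumptions, not taken from the documents.

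**The case against.** The strongest reply is that the search sentence does not say *only* serious events. The sentence just before it states the table's content plainly, so a careful programmer would include both kinds and the matter is editorial. This lowers the chance of harm but does not remove the defect. On that reading the SAP gives no search rule for the non-serious events, including whether broad or narrow scope applies to them, and the same deletion is needed.

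A second reply is that non-serious cytopenias remain visible elsewhere, and this stands:

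- They appear in the general TEAE tables by dose at onset and in the AE listing. Frequent terms could also appear in the table of non-serious TEAEs above the 5% threshold (SAP 11.2.3).
- Protocol 6.3, criterion 10, requires withdrawal for Grade 3 or higher laboratory values and for Grade 2 values that persist through two repeat tests, so such cases would also show in disposition.
- Under Protocol 6.4, referral to the data monitoring committee follows from withdrawal criteria being met, and SAP 4.5 puts that committee's outputs in a separate SAP. This table is not the stated trigger.

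What these outputs do not supply is the query-grouped count with EAIR and EAER by dose.

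Third, the numbers above are not specific to cytopenias. They are roughly 100 divided by subject-years, and the zero-event limit would be the same for any event in this study. That is correct. They scale the effect and do not predict it.

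Finally, the match with SAP 14.3.3 covers only the absence of a seriousness filter, since that search is narrow scope. SAP 14.3.5 matches in scope as well.

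**Conclusion.** The contradiction is real and should be corrected. It is a drafting error in an operational selection rule; no statistical method is in dispute. The content sentence, the parallel searches and Protocol 9.6 all point to *serious* in the search sentence as the word that is wrong.

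The consequence is limited to one descriptive special-monitoring table. If it were programmed from the search sentence, each subject with only non-serious cytopenias would be missing from that table, at the per-subject cost calculated above. With no serious case, the table would report a zero rate whatever the number of non-serious cases. The likely total understatement cannot be estimated because the documents give no cytopenia frequency. No hypothesis test or decision rule depends on the table. The any-TEAE rate and the laboratory outputs are unaffected.

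**What to change.** In the search sentence of SAP 14.3.4, delete the word *serious*. The search then takes all TEAEs that code to a broad- or narrow-scope term of the query. Leave the content sentence and the scope as they are. The program that flags cytopenia events should be checked against the corrected sentence before database lock.

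The cost is one word in the SAP, with no new data and no new output.

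Optionally, and for readability only, sections 11.2.3 and 14.3 could note that section 14.3.2.1, which leaves serious infections in the SAE tables, is an exception to the general statement that each special-monitoring topic is summarized separately. The correction does not depend on this.

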#### **14.3.5 Neuropsychiatric events**

This table is based on the SMQ of “Depression and suicide/self-injury” (all TEAEs that code to a PT included in the Scope=Broad and/or Scope=Narrow).

An external neuropsychiatric adjudication committee will evaluate potential neuropsychiatric events and determine whether any of those events were associated with suicidal ideation and behavior (SIB). If an event is adjudicated as SIB, further information will be provided. A separate listing for SIB events as determined by the adjudication committee will be included.

#### **14.3.6 Inflammatory bowel disease**

Inflammatory bowel disease events will be tabulated separately, based on the HLGT = ‘Colitis excl infective’.

#### **14.3.7 Anaphylactic reaction**

Anaphylactic reactions will be summarized together in a stand-alone table with the following incidence rows:

- The first row within the body of the table will be labeled ‘Any hypersensitivity/anaphylactic reaction’ and will represent the overall incidence of subjects who reported at least one hypersensitivity reaction or at least one anaphylactic reaction.
- The second row within the body of the table will be labeled ‘Any hypersensitivity reaction’ and will represent the overall incidence of subjects who reported at least one hypersensitivity reaction.
- The third row within the body of the table will be labeled ‘Any anaphylactic reaction’ and will represent the overall incidence of subjects who reported at least one anaphylactic reaction.

Following these three overall incidence rows, all TEAEs that have been identified as either a hypersensitivity reaction or an anaphylactic reaction will be summarized by SOC, HLT and PT (these will not be presented by subcategory).

Hypersensitivity reactions and anaphylactic reactions will be identified as follows:

- **Hypersensitivity reactions:** all TEAEs with onset (start date/time) within 24 hours after any administration of study medication, which code to a PT which contains the term 'hypersensitivity' will be considered to be a hypersensitivity reaction and included in the summary table
- **Anaphylactic reactions:** An algorithmic approach will be used to identify TEAEs that are considered to be anaphylactic reactions. Preferred terms are separated into 4 distinct categories (A, B, C, D) prior to the algorithmic approach being applied.

All TEAEs with onset (start date/time) within 24 hours after any administration of study medication, and which fulfill any of the 3 criteria described in [Section 14.3.7.1](#) will be included in the summary table.

Any TEAEs with missing start time will be assumed to have occurred at the time of or after dosing for this purpose, if the event date is on the same day as a dosing date.

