#### 14.3.7.1 Anaphylactic reaction algorithm

The SMQ = 'anaphylactic reaction' consists of 3 parts:

A **narrow search** containing PTs that represent core anaphylactic reaction terms. If a subject reports any TEAE which codes to a PT included in Category A, then the event will be flagged as an anaphylactic reaction and summarized as such in the table.

– Category A

5. Anaphylactic reaction
6. Anaphylactic shock
7. Anaphylactic transfusion reaction
8. Anaphylactoid reaction
9. Anaphylactoid shock
10. Circulatory collapse
11. Dialysis membrane reaction
12. Kounis syndrome
13. Shock
14. Shock symptom
15. Type I hypersensitivity

- A **broad search:** If a subject reports any TEAE which codes to a PT included in Category B **AND** reports any TEAE which codes to a PT included in Category C, **and both TEAEs have the same start date**, then both events will be flagged as anaphylactic reactions and summarized as such in the table.

– **Category B**

1. Acute respiratory failure
2. Asthma
3. Bronchial oedema
4. Bronchospasm
5. Cardio-respiratory distress
6. Chest discomfort
7. Choking
8. Choking sensation
9. Circumoral oedema
10. Cough
11. Cyanosis
12. Dyspnoea
13. Hyperventilation
14. Irregular breathing
15. Laryngeal dyspnoea
16. Laryngeal oedema
17. Laryngospasm
18. Laryngotracheal oedema
19. Mouth swelling
20. Nasal obstruction
21. Oedema mouth
22. Oropharyngeal spasm
23. Oropharyngeal swelling
24. Respiratory arrest
25. Respiratory distress
26. Respiratory dyskinesia
27. Respiratory failure
28. Reversible airways obstruction
29. Sensation of foreign body
30. Sneezing
31. Stridor

- 32. Swollen tongue
- 33. Tachypnoea
- 34. Throat tightness
- 35. Tongue oedema
- 36. Tracheal obstruction
- 37. Tracheal oedema
- 38. Upper airway obstruction
- 39. Wheezing

– **Category C**

- 1. Allergic oedema
- 2. Angioedema
- 3. Erythema
- 4. Eye oedema
- 5. Eye pruritis
- 6. Eye swelling
- 7. Eyelid oedema
- 8. Face oedema
- 9. Flushing
- 10. Generalised erythema
- 11. Injection site urticaria
- 12. Lip oedema
- 13. Lip swelling
- 14. Nodular rash
- 15. Ocular hyperaemia
- 16. Oedema
- 17. Periorbital oedema
- 18. Pruritis
- 19. Pruritis allergic
- 20. Pruritis generalised
- 21. Rash
- 22. Rash erythematous
- 23. Rash generalized

24. Rash pruritic
25. Skin swelling
26. Swelling
27. Swelling face
28. Urticaria
29. Urticaria papular

– **Category D**

1. Blood pressure decreased
2. Blood pressure diastolic decreased
3. Blood pressure systolic decreased
4. Cardiac arrest

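### The hypersensitivity row in SAP 14.3.7 cannot count isolated urticaria or angioedema, or any reaction starting more than 24 hours after a dose, so it understates the topic named in protocol 9.6

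*SAP*

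**What the plan says.** Protocol 9.6 lists the adverse events for special monitoring. The list includes "cytopenias, hypersensitivities, suicide ideation or behavior", and no term list or time window is attached to the hypersensitivity topic.

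SAP 11.2.3 and 14.3 carry the topic forward as hypersensitivity and anaphylactic reactions combined. SAP 14.3.7 is the only place where its terms are defined. It plans one stand-alone table with three overall rows (either kind of reaction, hypersensitivity, anaphylaxis), followed by the identified events by SOC, HLT and PT.

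- **Hypersensitivity.** The rule covers "all TEAEs with onset (start date/time) within 24 hours after any administration of study medication, which code to a PT which contains the term"; the word to be matched is 'hypersensitivity'.
- **Anaphylaxis.** Onset must fall within the same 24 hours, and the event must "fulfill any of the 3 criteria described in" SAP 14.3.7.1. First criterion: "If a subject reports any TEAE which codes to a PT included in Category A, then the event will be flagged as an anaphylactic reaction". Second: "If a subject reports any TEAE which codes to a PT included in Category B" and, with the same start date, "reports any TEAE which codes to a PT included in Category C". Third: a Category D term with a Category B or C term, again on the same start date.

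Category C runs from allergic oedema and angioedema to urticaria and "Urticaria papular".

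**The concern.** The hypersensitivity rule matches one word in the preferred term. The SAP's own Category C names allergic manifestations, yet the rule cannot reach any of them. The anaphylaxis rule reaches them only when they are paired with a respiratory or cardiovascular term on the same date. Skin and mucosal reactions on their own fall between the two definitions. The 24-hour condition then removes later events even when they are coded with the right word.

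What is at stake is how one table is read. At most 45 subjects are expected, so a special-monitoring row will rest on few subjects. A zero beside 'Any hypersensitivity reaction' invites the conclusion that no such reaction occurred. Nothing in the table would tell the reader that urticaria and angioedema were ineligible.

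**Working it through.** The plan gives no figure to reproduce, so the check applies the printed rules to the printed terms and to test cases.

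**Term lists in SAP 14.3.7.1, searched for the word 'hypersensitivity'**

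| Category | Terms | Containing the word |
|---|---|---|
| A | 11 | 1 (Type I hypersensitivity) |
| B | 39 | 0 |
| C | 29 | 0 |
| D | 8 | 0 |

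Allergic oedema, angioedema, injection site urticaria and urticaria are items 1, 2, 11 and 28 of Category C.

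**Test cases.** Hypersensitivity = onset within 24 hours and the word present. Anaphylaxis = onset within 24 hours and (A alone, or B with C on the same date, or D with B or C on the same date). 'Drug hypersensitivity' stands for any preferred term that contains the word.

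| Event(s) after a dose | Hypersensitivity row | Anaphylaxis row |
|---|---|---|
| Urticaria alone, 1 h | no | no |
| Angioedema alone, 1 h | no | no |
| Injection site urticaria alone, 1 h | no | no |
| Urticaria and angioedema, same date | no | no |
| Urticaria and dyspnoea, both within 24 h, different dates | no | no |
| Urticaria and dyspnoea, same date | no | yes |
| Angioedema and hypotension, same date | no | yes |
| Drug hypersensitivity, 1 h | yes | no |
| Drug hypersensitivity, 30 h | no | no |
| Type I hypersensitivity, 1 h | yes | yes |

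The word 'isolated' is essential: with a same-date Category B or D term, urticaria or angioedema does count, but as anaphylaxis. The rule for missing start times relaxes only the 24-hour condition on dosing days and does not touch the word match.

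**Width of the time window.** A completer has 12 dosing visits, Weeks 0 to 44 (SAP 7). TEAEs are collected to the last dose + 140 days (SAP 11.2.1), so the span is 44 × 7 + 140 = 448 days. Twelve 24-hour windows cover 12 / 448 = 2.7% of it. This describes the rule only. Reactions need not be spread evenly over time, so it does not estimate the share of events missed.

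**Comparison with other topics.** Malignancies, cytopenias, neuropsychiatric events and hepatic events (SAP 14.3.3, 14.3.4, 14.3.5, 14.3.8) are searched by SMQ, with no limit in hours after dosing.

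**The case against.** The strongest reply is that nothing is lost. SAP 11.2.3 tabulates every TEAE by SOC, HLT and PT and by dose at onset, and the AE listing shows onset time and days since the most recent dose. Three subjects with urticaria would appear as three subjects under that term. The primary variable, exposure-adjusted TEAE incidence, does not depend on this table, and no test is run on its rows. All of this stands, and it limits the point to one derived table. It does not make that table's label accurate.

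A reader might infer that the SAP breaches the protocol. It does not: protocol 9.6 names a monitoring topic, and protocol section 14 prescribes no hypersensitivity table, term list or window. The 24-hour condition also fits an intention to capture acute dosing reactions, and for that reason it deserves to survive as a sub-row. But the row is not labelled as acute reactions only, and the word match would miss acute urticaria in any case.

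A reader might also infer that the exposure-adjusted rates for these rows are biased. SAP 11.2.3 and 14.3 confine EAIR and EAER in special-monitoring tables to the 'Any TEAE' categories and do not say whether the three named rows qualify, so that step is not supported.

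Nor is a non-SMQ definition unusual in this SAP. Inflammatory bowel disease and fungal infections use high level group terms, opportunistic infections a sponsor list with physician review, and MACE adjudication. The SMQ topics show that the proposed remedy fits the plan's practice, not that the present rule is an anomaly.

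Finally, protocol 9.1.3 asks investigators to record a diagnosis rather than separate signs, so some allergic reactions will be entered under a term with the right word. That is partial mitigation. Urticaria and angioedema can themselves be recorded as the diagnosis, and nothing requires recoding.

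**Conclusion.** The point holds for the special-monitoring table. Followed exactly, SAP 14.3.7 leaves out of every row isolated urticaria, angioedema or allergic oedema, and any 'hypersensitivity' term starting after 24 hours. For the 'Any hypersensitivity reaction' row the direction is certain if the topic is read as including these events: the row can only understate. For the combined row the net direction is less clear, because the anaphylaxis algorithm can also admit nonspecific same-date pairs such as cough with rash.

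The size cannot be estimated, because the documents give no expected rate for these terms. As a scale only, if all 45 subjects enrol, each omitted subject is worth 1 / 45 = 2.2 percentage points in the all-subjects column. The conclusion does not extend to the primary TEAE analysis, the general TEAE tables or the listings. It is worth correcting before database lock, but it does not threaten the study's main result.

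**What to change.** In SAP 14.3.7:

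- Define the hypersensitivity row as all TEAEs in the narrow scope of the MedDRA Hypersensitivity SMQ, over the whole TEAE window.
- Beneath it, report the subset with onset within 24 hours of a dose as a sub-row, keeping the present rule for missing start times.
- Leave the anaphylaxis algorithm unchanged as its own row. A subject may appear in both rows, as already happens with Type I hypersensitivity; the combined row still counts that subject once.

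Do not widen the word match by adding the full Category A and C lists. That would count rash, erythema, oedema, shock and circulatory collapse as hypersensitivity on a single term, and would blur the line between the two rows.

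The documents do not reproduce the SMQ's contents, so the study team should confirm them in the MedDRA version named in the SAP (19.0) and check that the terms at issue here are covered.

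The cost is a short SAP amendment and one changed search. No new data are needed. The downside is that some nonspecific skin terms will appear in the table, which matters in a psoriasis population. Because the table lists events by preferred term, readers can see which terms drive the count.
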